# 3.2.3 Exploratory Objective Estimands

The estimands corresponding to the exploratory objectives are shown in Table 3 only for the endpoints to be assessed.

Table 3 Exploratory Objective Estimands

Table 5 Exploratory Objective Estimatios		
Objective 1	Mean reduction from the OP in the number of migraine days per month by pain intensity (total; moderate or severe) in each month and over the entire DBT Phase	
Efficacy Endpoint	Mean changes from OP in the number of migraine days per month during DBT (1) over time by month and (2) overall DBT, by pain intensity (total; moderate or severe)	
Summary	Mean changes from OP by treatment group using descriptive statistics and linear mixed effects model with repeated measures, and difference between treatment groups from model for the migraine analysis set	
Intercurrent Events	Study drug discontinuation: hypothetical strategy	
	Non-study prophylactic migraine medication use: treatment policy strategy	
	Nonstudy acute migraine-specific medication use: composite strategy	
	Use of nonstudy other medication to treat headache (migraine or nonmigraine) or aura: treatment policy strategy	
Objective 2	Proportions of subjects with $\geq 50\%$ reduction from the OP in the number of migraine days per month by pain intensity (total; moderate or severe) in each month and over the entire DBT Phase	
Efficacy Endpoint	Proportions of subjects with $\geq 50\%$ reduction from the OP in the number of migrained days per month during DBT (1) over time by month and (2) overall DBT, by pain intensity (total; moderate or severe)	
Summary	Percentages by treatment group, and difference in percentages between treatment groups using Mantel-Haenszel risk estimation with stratification by randomization stratum for the migraine analysis set	
Intercurrent Events	Study drug discontinuation: composite strategy	
	Non-study prophylactic migraine medication use: treatment policy strategy	
	Nonstudy acute migraine-specific medication use: composite strategy	
	Use of nonstudy other medication to treat headache (migraine or nonmigraine) or aura: treatment policy strategy	
Objective 6	Mean number of acute migraine-specific medication days per month in each month and over the entire DBT Phase	
Efficacy Endpoint	Mean number of acute migraine-specific medication days per month during DBT (1) over time by month and (2) overall DBT	

Summary	Mean values by treatment group using descriptive statistics and linear mixed effects model with repeated measures, and difference between treatment groups from model for the migraine analysis set
9	Study drug discontinuation: hypothetical strategy
1	Non-study prophylactic migraine medication use: treatment policy strategy
Intercurrent Events	Nonstudy acute migraine-specific medication use: not applicable
	Use of nonstudy other medication to treat headache (migraine or nonmigraine) or aura: treatment policy strategy
( Injective /	Mean number of acute migraine medication days per month in each month and over the entire DBT Phase
	Mean number of acute migraine medication days per month during DBT (1) over time by month and (2) overall DBT
Summary	Mean values by treatment group using descriptive statistics for the migraine analysis set
9	Study drug discontinuation: hypothetical strategy
1	Non-study prophylactic migraine medication use: treatment policy strategy
Intercurrent Events	Nonstudy acute migraine-specific medication use: not applicable
	Use of nonstudy other medication to treat headache (migraine or nonmigraine) or aura: not applicable
Uniective x	Frequency of LFT elevations based on fold changes above ULN in subjects treated with zavegepant during the DBT and OLE Phases
	Number and percentage of subjects with LFT elevations (ALT, AST, or TBL) based on fold changes above ULN on treatment
Siimmary	Frequency by treatment group for the DBT and OL zavegepant safety analysis sets with LFT data
9	Study drug discontinuation: while-on-treatment strategy
1	Non-study prophylactic migraine medication use: treatment policy strategy
Intercurrent Events	Nonstudy acute migraine-specific medication use: treatment policy strategy
	Use of nonstudy other medication to treat headache (migraine or nonmigraine) or aura: treatment policy strategy
Objective 9	Frequency of ALT or AST elevations > 3x ULN in temporal association with nausea, vomiting, anorexia, abdominal pain or fatigue in subjects treated with zavegepant during the DBT and OLE Phases
Safety Endpoint	Number and percentage of subjects in the safety analysis set with ALT or AST > 3x ULN concurrent with nausea, vomiting, anorexia, abdominal pain or fatigue on treatment
	Frequency by treatment group for the DBT and OL zavegepant safety analysis sets
9	with LFT data
	with LFT data Study drug discontinuation: while-on-treatment strategy

	Use of nonstudy other medication to treat headache (migraine or nonmigraine) or aura: treatment policy strategy
Objective 10	Mean changes from baseline in the MSQ preventive role function and emotional function domain scores at Week 12 of the DBT Phase
Outcomes Research Endpoint	Mean changes from baseline in the MSQ preventive role function and emotional function domain scores at Week 12 of the DBT Phase
Summary	Mean changes from baseline by treatment group using descriptive statistics for the DBT efficacy analysis set
Intercurrent Events	Study drug discontinuation: treatment policy strategy
	Non-study prophylactic migraine medication use: treatment policy strategy
	Nonstudy acute migraine-specific medication use: treatment policy strategy
	Use of nonstudy other medication to treat headache (migraine or nonmigraine) or aura: treatment policy strategy
Objective 11	Mean changes from baseline in the MIDAS absenteeism and presenteeism scores at Week 12 of the DBT Phase
Outcomes Research Endpoint	Mean changes from baseline in the MIDAS absenteeism and presenteeism scores at Week 12 of the DBT Phase
Summary	Mean changes from baseline by treatment group using descriptive statistics for the DBT efficacy analysis set
	Study drug discontinuation: treatment policy strategy
	Non-study prophylactic migraine medication use: treatment policy strategy
Intercurrent Events	Nonstudy acute migraine-specific medication use: treatment policy strategy
	Use of nonstudy other medication to treat headache (migraine or nonmigraine) or aura: treatment policy strategy
Objective 12	Mean changes from baseline in MSQ domain scores and MIDAS scores during the OLE Phase
Outcomes Research Endpoint	Mean changes from baseline in the (1) MSQ restrictive role function, preventive role function, and emotional function domain scores and (2) MIDAS total, absenteeism, and presenteeism scores at Weeks 24 and 64 of the OLE Phase
Summary	Mean changes from baseline by treatment group using descriptive statistics for the DBT efficacy analysis set
Intercurrent Events	Study drug discontinuation: treatment policy strategy
	Non-study prophylactic migraine medication use: treatment policy strategy
	Nonstudy acute migraine-specific medication use: treatment policy strategy
	Use of nonstudy other medication to treat headache (migraine or nonmigraine) or aura: treatment policy strategy

# 4 ANALYSIS SETS, TREATMENT GROUPS, AND SUBGROUPS

# 4.1 Analysis Sets

The following analysis sets are evaluated and used for presentation and analysis of the data:

- Enrolled: Subjects who sign an informed consent form and are assigned a subject identification number, i.e., nonmissing informed consent date. This analysis set is used mainly to assess study population and in by-subject listings.
- Full: Subjects in the enrolled analysis set who receive a randomized treatment assignment from the IWRS, i.e., nonmissing IWRS randomization date. This analysis set is used mainly to assess study population.
- Safety: Subjects in the enrolled analysis set who take ≥ 1 dose of study drug (zavegepant or placebo), i.e., nonmissing study drug start date. This analysis set is used to assess study population and produce select by-subject listings.
  - O DBT safety: Subjects in the safety analysis set who take ≥ 1 dose of DB study drug (zavegepant or placebo), i.e., nonmissing DB study drug start date. This analysis set is used to assess study population, exposure, and on-DBT safety.
  - OL zavegepant safety: Subjects in the safety analysis set who take ≥ 1 dose of OL zavegepant, i.e., nonmissing OL zavegepant start date. This analysis set is used to assess study population, exposure, and on-OL zavegepant safety.
    - Interim safety: Subjects in the OL zavegepant safety analysis set with OL zavegepant start date DB study drug last date > 7 days. This analysis set is used to assess post-DBT pre-OL zavegepant safety.
  - DB or OL zavegepant safety: Subjects in the safety analysis set who take ≥ 1 dose of DB or OL zavegepant, i.e., nonmissing DB or OL zavegepant start date. This analysis set is used to assess exposure and on-DB or OL zavegepant safety.
  - o Follow-up safety: Subjects in the safety analysis set whose last contact date is in the follow-up safety analysis period. This analysis set is used to assess follow-up safety.
- DBT efficacy: Subjects in the full analysis set who are randomized only once and take ≥ 1 dose of DB study drug (zavegepant or placebo). This analysis set is used mainly to assess DBT outcomes research.

Migraine: Subjects in the DBT efficacy analysis set with  $\geq 14$  days of eDiary efficacy data (not necessarily consecutive) in both the OP and  $\geq 1$  month (4-week interval) in the DBT Phase (see Section 6.3.1). This analysis set is used to assess migraine days, acute migraine-specific medication days, and acute migraine medication days

See Section 7.1 for derived dates and Section 7.2 for analysis periods.

## 4.2 Treatment Groups

Treatment groups in the DBT Phase are zavegepant 100 mg, zavegepant 200 mg, placebo 100 mg, and placebo 200 mg. OL zavegepant dose groups in the OLE Phase are zavegepant 100 mg and zavegepant 200 mg.

The safety analysis sets are assessed by as-treated treatment group (i.e., actual treatment received), the randomized, full, efficacy, and migraine analysis sets are assessed by as-randomized treatment group, and the enrolled analysis set is assessed overall.

If a subject takes  $\geq 1$  dose of planned randomized DB study drug, then that subject is considered to have as-treated treatment group equal to as-randomized treatment group (see Section 6.2.6.2).

If there are non-randomized subjects who take study drug, then the as-randomized treatment group of "not randomized" is included in the full analysis set augmented with the safety analysis set.

## 4.3 Subgroups

The following efficacy subgroups are of interest for the migraine analysis set:

• Stable prophylactic migraine medication use through randomization (i.e., randomization stratum): yes, no (see Section 6.2.5.4).

Randomization strata are based on the actual data, not those assigned by IWRS. Subgroup tables present results by subgroup level and overall for subjects with nonmissing subgroup level data.

## 5 SAMPLE SIZE, POWER, AND TYPE 1 ERROR

With a sample size of approximately 480 randomized subjects per zavegepant treatment group and 240 randomized subjects per placebo treatment group, we expect approximately 440 subjects per zavegepant treatment group and 220 subjects per placebo treatment group in the migraine analysis set. Assuming zavegepant provides a 1-day advantage over placebo pooled on the mean change in migraine days per month over the entire DBT Phase (Weeks 1 to 12), common standard deviation of 4.2 days, and a 2-sided  $\alpha = 0.025$  level, then the study has  $\geq 90\%$  power for the primary endpoint. The estimates for the migraine analysis set sample size, mean change in migraine days per month, and standard deviation (SD) are based on observed pooled data from rimegepant study BHV3000-305.

Type 1 error is not applicable. The significance of the primary and secondary endpoints will not be evaluated.

## 6 STATISTICAL ANALYSES

All statistical analyses are performed using SAS statistical software (Version 9.4 or higher).

#### 6.1 General

#### 6.1.1 Programmed Output

A list of TLFs and corresponding templates are presented separately in a mock TLF document corresponding to this SAP.

Refer to the Core SAP for additional details about programmed output.

#### 6.1.1.1 Tables

Treatment group presentation in tables by analysis set is shown in Table 4. Exceptions are specified in subsequent sections as needed.

Table 4 Treatment Group Presentation in Tables by Analysis Set

Analysis Set	Number of Columns	Abbreviated Treatment Group
Enrolled	1	Overall
Full, DBT efficacy, migraine, DBT safety, interim safety by treatment group, {zavegepant pooled}, {placebo pooled}, and {overall}	4 to 7	ZAV 100 mg ZAV 200 mg {ZAV Pooled} PBO 100 mg PBO 200 mg {PBO Pooled}
OL zavegepant safety by OL zavegepant dose and overall	3	{Overall} OL ZAV 100 mg OL ZAV 200 mg Overall
DB or OL zavegepant safety by DB or OL zavegepant dose and overall	3	DB ZAV or PBO 100 mg/OL ZAV 100 mg DB ZAV or PBO 200 mg/OL ZAV 200 mg Overall
Follow-up safety by treatment group/OL zavegepant status and overall	6	DB ZAV 100 mg/OL ZAV 100 mg DB ZAV 200 mg/OL ZAV 200 mg DB PBO 100 mg to OL ZAV 100 mg DB PBO 200 mg to OL ZAV 200 mg DB PBO Pooled No OL ZAV Overall

"ZAV Pooled" is defined as the DB zavegepant 100 mg and DB zavegepant 200 mg treatment groups combined. "PBO Pooled" is defined as the DB placebo 100 mg and DB placebo 200 mg treatment groups combined. "DB PBO X mg to OL ZAV X mg" denotes as-treated DB placebo X mg subjects in the OL zavegepant safety analysis set (X = 100 or 200), and "DB PBO Pooled No OL ZAV" denotes as-treated DB placebo pooled subjects not in the OL zavegepant safety analysis set; note that these 3 placebo groups add to the "PBO Pooled" group.

Results for study population also include overall treatment group (see Sections 6.2 and 6.4).

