4.3.3 Open-label Extension (OLE) Phase

The OLE Phase will be up to 52 weeks through the Week 64 or EOT Visit.

Note that the OLE Phase was added to the study design after some subjects already entered the Follow-up Phase after the DBT Phase. *Subjects who complete 12 weeks of the DBT Phase and have not entered the Follow-up Phase* may be offered to enter the OLE Phase. Subjects must meet the same laboratory eligibility criteria assessed prior to randomization in

the DBT Phase in order to be eligible for the OLE Phase. Repeat labs will not be allowed at the week 12 visit to determine OLE eligibility. The DBT Week 12 laboratory results will be used to assess eligibility for the OLE Phase. Once the Week 12 laboratory results are received and eligibility is confirmed, the subject should be contacted by telephone and instructed to start taking open-label study drug.

Subjects who (1) discontinue early from the DBT Phase or (2) have already entered the Follow-up Phase are not eligibile to enter the OLE Phase.

Eligible subjects will have study visits approximately every 2 weeks during the first month of the OLE Phase and then every 4 weeks, through Week 64. See Table 2 for schedule of procedures.

Subjects randomized to zavegepant 100 mg or matching placebo in the DBT Phase will receive open-label zavegepant 100 mg in the OLE Phase. Subjects randomized to zavegepant 200 mg or matching placebo in the DBT Phase will receive open-label zavegepant 200 mg in the OLE Phase.

At each visit, the study drug wallet will be reviewed for compliance and concomitant medication use will be reviewed (and compared to concomitant medication paper diary entries, where applicable). Subjects will be dispensed additional study drug as needed. Additional safety assessments (including laboratory tests and ECGs) will be performed per the schedule outlined in Table 2.

Subjects will not use the eDiary in the OLE Phase.

Subjects must continue to record use of concomitant medications in the concomitant medication paper diary through the entire OLE Phase.

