4.3.4.1 Follow-up Week 2 Visit

Subjects will return to the study site approximately 2 weeks (14 days +/- 2 days) after the last visit in the last treatment phase to collect LFTs, CK, vital signs, electrocardiography, and assessment of AEs/ SAEs. Subjects will return the concomitant medication paper diary which should be reviewed one final time by study staff.

Investigators should assess subjects for AEs consistent with study drug dependency or withdrawal effects and report as appropriate (see Section 7.4).

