## 6.2.3.5 Subject Disposition during the Follow-up Phase

The frequency table of subject disposition during the Follow-up Phase is provided by as-treated treatment group/OL zavegepant status and overall for the follow-up safety analysis set based on the Follow-up Subject Status CRF, and displays the following categories:

- Did not formally enter the Follow-up Phase. These are identified as subjects with missing response to the question "Did the subject complete the Follow-up Phase?", and any of the following:
  - "No" response to the question "Is the subject continuing to the Follow-up Phase?" and missing response to the question "Is the subject continuing to the next phase?" on the DB Subject Status CRF
  - "No" response to the question "Is the subject continuing to the next phase?" on the DB Subject Status CRF
  - o "No" response to the question "Is the subject continuing to the Follow-up Phase?" on the OLE Subject Status CRF.

A footnote explains that these are subjects with data in the follow-up safety analysis period who did not continue to the Follow-up Phase as per DB or OLE Subject Status CRF.

- Ongoing in the Follow-up Phase. These are identified as subjects with missing response to the question "Did the subject complete the Follow-up Phase?", and who are not already categorized as "Did not formally enter the Follow-up Phase".
  - This category only exists before the final database lock. After the final database lock, these subjects are categorized as "Did not complete the Follow-up Phase".
- Completed the Follow-up Phase. These are identified as subjects with "yes" response to the question "Did the subject complete the Follow-up Phase?".
- Did not complete the Follow-up Phase. These are identified as subjects with "no" response to the question "Did the subject complete the Follow-up Phase?".

o Reasons for not completing the Follow-up Phase, including not reported

0

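### The follow-up safety tables split double-blind placebo subjects by open-label status but not double-blind zavegepant subjects, so the placebo column without open-label drug has no zavegepant counterpart

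*SAP*

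**What the plan says.** SAP Table 4 (Section 6.1.1.1) titles the row "Follow-up safety by treatment group/OL zavegepant status and overall", so open-label status is a declared classifier. The columns are:

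1. `DB ZAV 100 mg/OL ZAV 100 mg`
2. `DB ZAV 200 mg/OL ZAV 200 mg`
3. `DB PBO 100 mg to OL ZAV 100 mg`
4. `DB PBO 200 mg to OL ZAV 200 mg`
5. `DB PBO Pooled No OL ZAV`
6. `Overall`

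The text below the table defines columns 3 to 5. The fifth "denotes as-treated DB placebo pooled subjects not in the OL zavegepant safety analysis set", and the SAP adds "note that these 3 placebo groups add to the" pooled placebo group. No definition or adding-up statement covers columns 1 and 2.

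SAP 4.1 puts a treated subject in the follow-up safety set when the last contact date falls in the follow-up period, whether or not open-label drug was taken. SAP 6.2.3.5 presents follow-up disposition "by as-treated treatment group/OL zavegepant status and overall for the follow-up safety analysis set", and SAP 6.4 gives the same layout for the follow-up safety tables.

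On the purpose of follow-up, Protocol 4.3.4.1 states for the Week 2 visit: "Investigators should assess subjects for AEs consistent with study drug dependency or withdrawal effects and report as appropriate".

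**The concern.** Zavegepant subjects without open-label drug exist by design. Under Protocol 4.3.3, early discontinuers from the double-blind phase and subjects who fail the Week 12 laboratory criteria cannot enter the extension. Some completers could not enter either: "Note that the OLE Phase was added to the study design after some subjects already entered the Follow-up Phase after the DBT Phase".

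Among subjects who entered the extension, everyone in follow-up is coming off zavegepant. Within the Follow-up Phase, subjects never exposed to zavegepant are found only among placebo non-entrants. Their natural counterpart is the zavegepant non-entrants, who had at most about 12 weeks of drug. The layout isolates the first group and not the second.

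What is at stake is whether the planned follow-up tables can show an excess of events after stopping zavegepant. The tables concerned are the AE overview (SAP 6.4.1.2), AEs and SAEs (6.4.1.5), laboratory abnormalities (6.4.2.1), LFT elevations (6.4.2.2), vital sign and ECG abnormalities (6.4.3.2, 6.4.4.2) and C-SSRS (6.4.5).

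**Working it through.** **Column count.** Two zavegepant, two placebo-to-open-label, one placebo without open-label, and Overall: 2 + 2 + 1 + 1 = 6. This matches the stated 6, and none of them isolates zavegepant subjects without open-label drug.

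**Where those subjects go.** Two readings are possible.

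- *Merged.* Another Table 4 row, for the DB or OL zavegepant safety set, has the label "DB ZAV or PBO 100 mg/OL ZAV 100 mg". That set needs only one dose of double-blind or open-label zavegepant, and SAP 4.1 says of it: "This analysis set is used to assess exposure and on-DB or OL zavegepant safety". It therefore includes zavegepant subjects who took double-blind drug only, and its dose columns make sense only if the slash covers them. Carried over to the follow-up row, columns 1 and 2 hold all double-blind zavegepant subjects of that dose. This is the likelier reading.
- *Literal.* If the slash means that both were taken, these subjects are counted only under Overall.

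**Planned size.** Inputs: about 1440 randomized and about 1200 entering the extension (Protocol 5.1); allocation 480/480/240/240 (Protocol 1.4.1).

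- Non-entrants: 1440 − 1200 = 240, or 240/1440 = 16.7%.
- Equal non-entry across arms (assumption): 240 × 960/1440 = 160 zavegepant (80 per dose) and 240 × 480/1440 = 80 placebo.
- If the zavegepant non-entry rate is r times the placebo rate p, then p = 240/(960r + 480):

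| r (assumed) | p | Zavegepant non-entrants (960rp) | Placebo non-entrants (480p) |
|---|---|---|---|
| 0.5 | 0.250 | 120 | 120 |
| 1.0 | 0.167 | 160 | 80 |
| 1.5 | 0.125 | 180 | 60 |

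**Effect on the columns, at r = 1.**

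- Merged: each zavegepant column holds 400 entrants and 80 non-entrants, so non-entrants are 80/480 = 16.7% of it. With assumed follow-up AE rates of 10% in non-entrants and 5% in entrants, the column shows (80 × 0.10 + 400 × 0.05)/480 = 5.8%.
- Literal: the five group columns sum to 400 + 400 + 200 + 200 + 80 = 1280, against an Overall of 1440. The shortfall is the 160.

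**What a separate column could show.** For 160 against 80 subjects with a common event rate q, the 95% half-width is 1.96 × √[q(1 − q)(1/160 + 1/80)]. At assumed q of 5%, 10% and 20% this gives 5.8, 8.1 and 10.7 percentage points. Only fairly large differences would stand out.

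**Whether another planned table fills the gap.**

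| Display | Why it does not |
|---|---|
| On-DBT safety tables | While-on-treatment data end 7 days after discontinuation (SAP 3.2); the Follow-up Week 2 window opens at follow-up day 8 (SAP Table 5) |
| Interim safety AE overview (SAP 6.4.1.2) | By arm with placebo pooled, but limited to subjects who later took open-label drug after a gap of more than 7 days (SAP 4.1) |
| Laboratory and vital-sign change tables (SAP 6.4.2.3, 6.4.3.1) | Follow-up visits by treatment group without open-label status, so placebo columns mix exposed and never-exposed subjects |

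**The case against.** The case against is substantial, and several parts of it stand.

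*It is tempting to infer that placebo-controlled information after stopping drug is lost.* The documents do not support that. For non-entrants, the first 7 days after stopping fall in the on-DBT tables by arm, and later extension entrants have the interim AE overview. The data also survive: the AE listing covers all enrolled subjects (SAP 6.4.1), listings carry randomized arm and analysis period (6.1.1.2), and analysis-set membership is listed by subject (6.2.1). The comparison can be rebuilt, but it is not tabulated.

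*Nor are events in early discontinuers hidden.* AEs leading to discontinuation are tabulated by arm (6.4.1.3). Narrative identifiers cover follow-up SAEs and non-serious AEs leading to discontinuation in zavegepant-exposed subjects (6.4.6). The LFT listing shows all results over time for subjects with select elevations (6.4.2).

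*The matched pair is not a randomized comparison.* Extension entry is decided after randomization, by completion, laboratory results and amendment timing. This stands and needs a footnote. It applies equally to the placebo column already planned.

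*No stated objective depends on it.* Safety objectives 7 to 9 concern the double-blind and open-label phases, with on-treatment endpoints. The Week 2 instruction is for assessing individual subjects and plans no between-arm test. This stands and limits the weight of the point.

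*On the merged reading nobody is omitted, and the layout simply separates exposed from never-exposed subjects.* That is coherent, but the SAP does not say it, and it still sets a short-exposure placebo group beside zavegepant columns dominated by longer exposure. The Core SAP and mock tables were not available and might define the labels.

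*The SAP was amended after termination to reduce output* (SAP Section 1). This is a fair reason to prefer one pooled column to two.

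**Conclusion.** The point holds as a gap in the layout. Open-label status is applied to double-blind placebo subjects and not to double-blind zavegepant subjects, and the two zavegepant labels are undefined. The only concurrent placebo comparison within the Follow-up Phase itself is therefore absent from the planned tables. It should be corrected because the remedy is cheap and makes an existing column interpretable. It does not affect the efficacy analyses or the on-treatment safety results.

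The figures of about 160 zavegepant and 80 placebo non-entrants (120 to 180 and 120 to 60 over the range tried) rest on planned enrolment, planned extension entry and an assumed split across arms. They are not forecasts of table counts: the study was terminated in December 2023, and the follow-up set requires treatment and a last contact in follow-up. The merged reading is an inference from the slash in another row.

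**What to change.** In SAP Table 4, for the follow-up safety row:

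- Define the first two columns as double-blind zavegepant subjects, by dose, who are in the OL zavegepant safety analysis set.
- Add `DB ZAV No OL ZAV` beside `DB PBO Pooled No OL ZAV`. A single pooled column gives 7 columns and one per dose gives 8.
- State that the zavegepant columns add to pooled zavegepant, as is already done for placebo.
- Footnote that extension entry is a post-randomization event and that the comparison is descriptive.

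Apply this to the follow-up tables in SAP 6.2.3.5, 6.4.1.2, 6.4.1.5, 6.4.2.1, 6.4.2.2, 6.4.3.2, 6.4.4.2 and 6.4.5. The cost is a few lines of SAP text and one or two small columns in existing tables. No new data are needed. The drawback is more output in a plan that was being shortened, with wide uncertainty in the added columns.
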